2.3. Hypotheses

Primary Hypotheses

1. After 8-12 days of lens wear, the distance, binocular, high luminance, high contrast visual performance of the two test lenses will be superior to +0.01 logMAR.
2. After 8-12 days of lens wear, the near, binocular, high luminance, high contrast visual performance of the two test lenses will be superior to +0.17 logMAR.

Secondary Hypothesis

1. After 8-12 days of lens wear, the overall quality of vision of the two test lenses will be superior to 32 CLUE points.

Other Hypotheses: Not applicable.

3. TARGETED STUDY POPULATION

3.1. General Characteristics

Healthy male and female volunteers who are presbyopic will be recruited for the study. The subjects will all be adapted wearers of soft contact lenses in both eyes.

3.2. Inclusion Criteria

Potential subjects must satisfy all of the following criteria to be enrolled in the study:

1. The subject must read, understand, and sign the STATEMENT OF INFORMED CONSENT and receive a fully executed copy of the form.
2. The subject must appear able and willing to adhere to the instructions set forth in this clinical protocol.
3. The subject must be between at least 40 years of age and not greater than 70 years of age.
4. The subject's distance spherical equivalent refraction must be in the range of +3.75 D to -3.75 D.
5. The subject's refractive cylinder must be ≤ -0.75 D in each eye.
6. The subject's ADD power must be in the range of +0.75 D to +2.50 D in each eye.
7. The subject must have best corrected visual acuity of 20/20⁻³ or better in each eye.
8. The subject must own a pair of wearable spectacles if required for their distance vision.
9. The subject must be an adapted soft contact lens wearer in both eyes (i.e. worn lenses a minimum of 2 days per week for at least 8 hours per wear day, for 1 month or more duration).
10. The subject must either be wearing a presbyopic contact lens correction (e.g., reading spectacles over contact lenses, multifocal or monovision contact lenses, etc.) or respond positively to at least one symptom on the "Presbyopic Symptoms Questionnaire".

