1.2. Intended Use of Investigational Products

The intended use of the lenses is to correct distance spherical refractive error and presbyopia. Greater details on each of the marketed products can be found in the package insert in the appendices of this protocol.

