1.12	Pupillometry	The pupil measurements will be performed OD and OS under bright illumination (7.3-7.9 EV) and dark illumination (≤ 0 EV) using a Neuroptic Pupillometer or similar instrument. The room illuminance will be measured for each condition using the Sekonic lightmeter or similar instrument.	████████
1.13	Keratometry	Keratometry will be performed OD and OS recording the steep and flat dioptric power, corresponding meridians and clarity of mires.	████████
1.14	Subjective Sphero-cylindrical Refraction	An optimal, binocular balanced distance sphero-cylindrical refraction will be performed. Record the refraction and distance visual acuity to the nearest letter. Note: Best distance visual acuity with sphero-cylindrical refraction must be at least 20/20⁻³ in each eye for the subject to enroll in the study.	████████
1.15	Near ADD Determination	The near reading addition will be determined using the binocular crossed cylinder technique at 40 cm followed by optimization in a trial frame in step 1.17 below.	████████
1.16	Ocular Dominance	Determine the distance ocular dominance with the best distance correction in place using a +1.00-blur test. If the results are equivocal use the sighting dominance test to determine the dominant eye used for the study	Appendix E
1.17	Add Refinement	Place the BCC result in the trial frame and refine the near prescription with trial lenses (or flippers) under binocular conditions.	████████
1.18	Near Visual Acuity	Using the ETDRS 2000 Series Chart 1 or 2 near card placed at 40 cm. Record the near visual acuity OD, OS and OU at 40 cm.	

1.19	Biomicroscopy	
FDA Slit Lamp Classification Scale will be used to grade the findings and determine eligibility.
 
For the conjunctival redness (██████████) 0.5 unit increments will be used in the grading. Corneal Staining Assessment (██████████) will be graded in 1.0 increments.
 
If the clearance of the fluorescein needs to be expedited, preservative-free rewetting drops or saline may be instilled.
	██████████ ██████████ ██████████
1.20	Eligibility after Baseline	
All responses to Inclusion Criteria questions must be answered “yes” and all responses to Exclusion Criteria questions must be answered “no” for the subject to be considered eligible.
 
Determine whether the subject is eligible to participate in the study based on the examination findings. If so, proceed to lens fitting. If not, complete the final evaluation and discharge the subject.
	

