Visit 1: Treatment 1 Lens Fitting			
Step	Procedure	Details	██████████
1.21	Randomization ID	Record the Randomization ID per the random scheme.	
1.22	Lens Selection	Select the lens pair and power based on the randomization table and appropriate fitting guide for each eye. Record the test lens parameters (power and lot number).	Appendix G or H Fitting Guides
1.23	Lens Insertion	The Investigator or the subject inserts the study lenses. Record the time of lens insertion. Check for lens damage under the slit lamp before proceeding with lens settling. Replace damaged lenses if applicable. Worn, damaged lenses must be saved in saline and a product complaint form completed.	
1.24	Lens Settling	Allow the study lenses to settle for a minimum of 10 minutes.	
1.25	Visual Satisfaction	Determine if the subject’s vision is acceptable with the lenses. Allow the subject to look	

		down a hallway or out of a window for distance vision assessments, and for them to read a book, magazine or similar for near vision.	
1.26	Distance and Near Visual Acuity	
Measure the distance and near visual acuity OD, OS and OU. Record the results.
 
Note: Use the ETDRS 2000 Series Chart 1 or 2 near card placed at 40 cm to measure the Near visual acuity
	██████████
1.27	Over-refraction	
Perform a distance over-refraction OD and OS using loose lenses outside of the phoropter under ambient room illumination. The distance over-refraction may also be refined under binocular conditions. Record the results.
 
The results of the distance over-refraction may also be checked for the impact on near vision under monocular and/or binocular conditions.
	
1.28	Lens Fit Assessment	
Evaluate and grade lens centration, primary gaze movement, upgaze movement and tightness (push-up test). The subject will not proceed to wear the lenses if any of the following is observed:
 
 • presence of limbal exposure (appearance of clear cornea) in any gaze • presence of edge lift • presence of unacceptable movement (excessive or insufficient) in all three movement categories (primary gaze, upgaze, and push-up). 
If either lens is deemed unacceptable, the subject will be discontinued from the study. Remove the lenses, perform a slit-lamp evaluation, and complete the Final Evaluation form.
	██████████

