1.29	Modifications	
If the subjects vision is unacceptable for at least one distance or the Investigator determines that the visual acuity or over-refraction are not acceptable then a lens modification must be made. Up to two attempts at modification are
	
Appendix G or H
 
Fitting Guides

		permitted if necessary, in order to achieve an acceptable distance and near binocular performance for the subject, and to enable them to wear that particular lens type. Follow the appropriate fitting guide allowing for at least 10 minutes of settling time between each lens modification attempted. If modifications are required steps 1.22-1.28 will be repeated for each modification.	
1.30	PRO Post-Fit Questionnaire	The subject will evaluate the vision characteristics, comfort characteristics, handling characteristics, and visual symptoms of the study lenses using the PRO questionnaire.	
1.31	Exit Distance and Near Visual Acuity	Distance and near Snellen visual acuity will be measured for each eye with the study contact lenses in place. For near measures use the ETDRS 2000 Series Chart 1 or 2. The acuity will be recorded to the nearest letter OD, OS and OU. Note: The distance visual acuity must be at least 20/30 OU for the lenses to be dispensed.	██████████
1.32	Dispensing Criteria	The lenses will be dispensed for 2-4 days. 
 • Distance Snellen acuity equal to or better than 20/30 OU • Subject must indicate that the vision is acceptable. • Subject must indicate that the comfort of the lenses is acceptable. • Lenses must have an acceptable general lens fit. 	
1.33	Subject Instructions	Instruct the Subject the following: 
 • The lenses will be worn on a daily wear basis. • Only enough lenses will be dispensed to the subject to wear for the required number of days until their follow-up visit. No additional lenses will be dispensed. • A new lens will be opened and worn each day. • Instruct the subject to bring back all Unworn study lenses • Instruct the subject no cleaning or 	

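### Inclusion criterion 5 is wrong as written: in minus-cylinder form it admits -0.75 D and anything stronger, sets no upper limit, and refuses eyes with 0 to -0.50 D

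*Combined protocol and SAP*

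**What the plan says.** Criterion 5 in Section 3.2 states that the "refractive cylinder must be ≤ -0.75 D in each eye". The synopsis has the same words, so neither place corrects the other. Neither gives a second bound, a magnitude sign or a sign convention.

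The neighbouring criteria are written differently. Criterion 4 says the "distance spherical equivalent refraction must be in the range of +3.75 D to -3.75 D", and criterion 6 says the "ADD power must be in the range of +0.75 D to +2.50 D in each eye". Both name two ends.

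Eligibility is applied item by item. Visit 1, step 1.20 in Section 7.2 says "All responses to Inclusion Criteria questions must be answered" yes for the subject to be eligible.

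Section 1.2 gives the purpose of the lenses: "The intended use of the lenses is to correct distance spherical refractive error and presbyopia". The appended Test 1 fitting guide (Appendix H) lists cylinder below 1.00 D among the marks of an ideal multifocal candidate, and 1.00 D or more as less than ideal. The Test 1 package insert (Appendix C) covers up to about 1.50 D of astigmatism that does not interfere with acuity.

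**The concern.** With signed numbers, less than or equal to -0.75 means more negative, which in minus-cylinder form means more astigmatism. The inequality therefore appears to point the wrong way for a study of lenses that correct spherical error and presbyopia. It turns away the eyes with the least astigmatism and puts no ceiling on the rest.

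This is an operative threshold, and other parts of the plan depend on it. Section 8.1 makes eligibility a condition of completing the study. Section 14.1 places all analyses on the per-protocol population. Section 14.3 builds that population from completers without substantial deviations. Section 20 lets the sponsor withhold payment when an ineligible subject is continued. A monitor or an eCRF check that applies the text, and a clinician who applies the presumed intent, would classify the same subject in opposite ways.

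**Working it through.** There is no sample size, power or alpha figure to reproduce. The check applies the inequality to cylinder values and then asks whether anything else in the plan supplies the missing limit.

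**Step 1. Sign convention.** The protocol does not state one. In plus-cylinder form every value is 0 or greater, so none satisfies ≤ -0.75 D and nobody could enrol. The threshold is usable only in minus-cylinder form. The prescriptions in the Test 1 fitting guide are written that way (for example -4.50 D -1.00 x 180).

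**Step 2. Who passes.** In 0.25 D steps:

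| Cylinder (D) | Literal: cyl ≤ -0.75 | Magnitude: size of cyl ≤ 0.75 |
|---|---|---|
| 0, -0.25, -0.50 | refused | admitted |
| -0.75 | admitted | admitted |
| -1.00, -1.25, -1.50 and stronger | admitted | refused |

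The two readings share one value, -0.75 D. This counts dioptre values for illustration; it says nothing about how many subjects fall at each.

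**Step 3. Does criterion 4 cap the cylinder?** It limits spherical equivalent only. By the formula in the Test 1 guide, SE = sphere + cylinder/2. The following all have SE = -1.00 D, inside +3.75 to -3.75 D:

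- cylinder -1.00, sphere -0.50: -0.50 - 0.50 = -1.00
- cylinder -1.50, sphere -0.25: -0.25 - 0.75 = -1.00
- cylinder -3.00, sphere +0.50: +0.50 - 1.50 = -1.00
- cylinder -4.00, sphere +1.00: +1.00 - 2.00 = -1.00

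So criterion 4 supplies no cap.

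**Step 4. Does criterion 7 cap it?** Step 1.14 says "Best distance visual acuity with sphero-cylindrical refraction must be at least" 20/20 minus three letters. Acuity is tested with the cylinder corrected, so this does not limit the cylinder either.

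**Step 5. Exclusion criteria (Section 3.3).** None names cylinder or astigmatism.

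**Step 6. Later checks.** Step 1.25 asks whether the subject's "vision is acceptable with the lenses". Step 1.29 allows up to two modifications, "permitted if necessary, in order to achieve an acceptable distance and near binocular performance for the subject". Step 1.32 requires binocular distance acuity of 20/30 or better and acceptable vision before dispensing, and Section 8.2 withdraws subjects not dispensed because of poor vision. These may remove some highly astigmatic subjects. They follow randomization at step 1.21, act on achieved vision rather than cylinder, and cannot bring back low-cylinder eyes already refused at step 1.20.

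**Step 7. Comparison with the appendix.** The Test 1 guide states its limit as an unsigned size: below 1.00 D is ideal. Literal criterion 5 refuses 0 to -0.50 D, all inside that ideal range, and admits -1.00 D and stronger, all outside it.

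**The case against.** The strongest reply is practical. An eye-care investigator will very probably see a limit on low astigmatism and apply it as a magnitude, precisely because refusing eyes with no cylinder makes little sense here. The population implied by the literal text may then never arise. Step 1.14 records the refraction, so who meets which reading can be established afterwards. The study is an exploratory pilot (Section 14.4), and no planned calculation changes. All of this stands, and it limits the weight of the point. It does not make the text right: it means that eligibility depends on staff setting aside the written rule.

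Redaction is a fair caution too. The distance refraction procedure (Appendix I) and the protocol's Biotrue fitting guide (Appendix G) are blacked out, and a sign convention may be stated there. The minus-cylinder powers in the Test 2 package insert are weak evidence, since they belong to an astigmatism lens not used in this study. Criterion 5 itself, however, is fully visible in both places.

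A reader might infer more than the documents support:

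- *That the literal rule breaches the lens labelling.* It does not follow. Section 1.2 does not bar astigmatic eyes, the Test 1 insert covers up to about 1.50 D, and less than ideal in the guide is fitting advice, not a contraindication.
- *That most subjects would be misclassified.* The two readings differ on 6 of 7 grid values from 0 to -1.50 D and on 12 of 13 from 0 to -3.00 D. The ratio depends on where the grid stops and estimates no share of subjects. The guide's worked multifocal examples do not help, since both patients fall outside criterion 4 in at least one eye.
- *That sites would enrol inconsistently.* The number of sites is unclear. Sections 3.4 and 14.2 read as one site, while the synopsis and Section 5.1 suggest several.

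**Conclusion.** The criterion is wrong as written and should be corrected. Confidence is high on the inequality itself, which is plain arithmetic on visible text that appears twice, with no visible eligibility criterion to repair it. The one inference is minus-cylinder form, and the alternative would admit nobody.

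The size of the practical effect is unknown. The documents give neither a cylinder distribution nor the reading that staff will use, so neither the number of subjects affected nor any shift in logMAR can be derived. It would go too far to say that the study will enrol the wrong population. That assumes both literal application and a particular intent, and the sponsor's intent is not stated. Disputed deviations and changes to the per-protocol set are possible, not shown; Section 14.3 removes only substantial deviations, and nothing indicates how the committee would treat these cases. This is a necessary wording correction to an eligibility threshold in an exploratory pilot. It threatens no confirmatory claim.

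**What to change.** 1. The sponsor confirms the intended cylinder limit.
2. Restate criterion 5 in the synopsis and in Section 3.2, either as a magnitude or as a signed range with both ends, in the style of criteria 4 and 6. If a ceiling on low astigmatism was meant, one form would be: magnitude of refractive cylinder 0.75 D or less in each eye (0.00 to -0.75 D in minus-cylinder form). If another limit was meant, the same format serves.
3. State the sign convention next to the number.
4. Align the eligibility question and any eCRF check with the new wording.
5. If enrolment has begun, record before database lock which reading governs eligibility and per-protocol status, and apply it to the refraction recorded at step 1.14.

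The cost is one line in two places plus the form alignment. No extra data, visits or analyses are needed.

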3.3. Exclusion Criteria

Potential subjects who meet any of the following criteria will be excluded from participating in the study:

1. Ocular or systemic allergies or disease, or use of medication which might interfere with contact lens wear.
2. Pregnancy or lactation.
3. Currently diagnosed with diabetes.
4. Infectious diseases (e.g. hepatitis, tuberculosis) or an immune-suppressive disease (e.g. HIV).
5. Clinically significant (Grade 3 or 4) corneal edema, corneal vascularization, corneal staining, tarsal abnormalities or bulbar injection, or any other corneal or ocular abnormalities which would contraindicate contact lens wear.
6. Entropion, ectropion, extrusions, chalazia, recurrent styes, dry eye, glaucoma, history of recurrent corneal erosions.
7. Any previous, or planned, ocular or intraocular surgery (e.g., radial keratotomy, PRK, LASIK, lid procedures, cataract surgery, retinal surgery, etc.).
8. A history of amblyopia, strabismus or binocular vision abnormality.
9. Any ocular infection or inflammation.

10. Any ocular abnormality that may interfere with contact lens wear.
11. Use of any ocular medication, with the exception of rewetting drops.
12. History of herpetic keratitis.
13. Participation in any contact lens or lens care product clinical trial within 30 days prior to study enrollment.
14. Employee of clinical site (e.g., Investigator, Coordinator, Technician)

3.4. Enrollment Strategy

Study subjects will be recruited from the clinical site's subject database.

4. STUDY DESIGN AND RATIONALE

4.1. Description of Study Design

This is a single-masked, crossover, randomized, dispensing clinical trial. A total of approximately 60 eligible subjects will be targeted to complete the study. The subjects will be randomized and fit in the study lens and wear each lens type for approximately three days then undergo optimization, if required, and wear the optimized pair for approximately 1 week. The primary endpoint is visual performance. The secondary endpoint is the CLUE vision score.

4.2. Study Design Rationale

The study is a prospective, bilateral, crossover evaluation. As we have no historical clinical data on the lenses being tested the study design includes a washout period to minimize any potential carry-over effect.

4.3. Enrollment Target and Study Duration

Approximately 80 subjects will be recruited (40 myopes and 40 hyperopes) with an aim of completing a total of 60 subjects in the final cohort.

5. TEST ARTICLE ALLOCATION AND MASKING

5.1. Test Article Allocation

The study lenses will be worn in a bilateral and random fashion using a 2x2 crossover design with 2 lens types and 2 periods. Using a computer-generated randomization scheme provided by the study biostatistician, each subject will randomly be assigned to one of two unique sequences of the two lens types (Test1/Test2 or Test2/Test1). Randomization will be stratified by site.

Permuted block randomization will be used to avoid bias in the assignment of subjects to treatment, and to enhance the validity of statistical comparisons across treatment groups. Each block will contain two different lens trial sequences.

The order of lens wear will be based on the randomization scheme assigned to the study site. The study site will follow the randomization scheme provided and will complete enrollment according to the randomization list and will not pre-select or assign subjects.

This is a single masked study: subjects will be masked to the identities of the study lenses.

5.2. Masking

Masking will be used to reduce potential bias. Subjects will be unaware of the identity of the investigational product. Investigators and clinical site personnel involved in the data collection will not be masked as to the identity of the investigational product.

Under normal circumstances, the mask should not be broken until all subjects have completed the study and the database is finalized. Otherwise, the mask should be broken only if specific emergency treatment/course of action would be dictated by knowing the treatment status of the subject. In such cases, the Investigator may, in an emergency, contact the medical monitor. In the event the mask is broken; the Sponsor must be informed as soon as possible. The date, time, and reason for the unmasking must be documented in the subject record. The Investigator is also advised not to reveal the study treatment assignment to the clinical site or Sponsor personnel.

Subjects who have had their treatment assignment unmasked are expected to return for all remaining scheduled evaluations. Subjects who are discontinued may be replaced.

5.3. Procedures for Maintaining and Breaking Randomization Codes

The test articles mask shall not be broken unless information concerning the lens type is necessary for the urgent medical treatment of a subject. The Sponsor must be notified before the mask is broken.

When dispensing test articles, the following steps should be followed to maintain randomization codes:

1. Investigator or designee (documented on the Delegation Log) will consult the lens fitting schedule/randomization scheme to obtain the test article assignment for that subject prior to dispensing
2. Investigator or designee will record the subject's number on the appropriate line of the randomization scheme.
3. Investigator or designee will pull the appropriate test articles from the study supply. All test articles that are opened, whether dispensed (placed/fit on eye or dispensed outside the clinical site) or not, must be recorded on the Test Article Accountability Log in the "Dispensed" section

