14.2. Sample Size Justification

A total of approximately 80 eligible subjects will be enrolled into the study at this site and at least 60 subjects will complete this study. This is a pilot study for assessing the test articles. As such, the sample size calculation was not based on any power analysis with regard to the primary endpoint. The collected data will be used to design future trials.

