14.4. Level of Statistical Significance

All planned analysis for this study will be conducted with an overall type I error rate of 5%. No adjustment for multiple comparisons will be conducted unless specified otherwise. This is a pilot study and all the hypotheses are exploratory in nature.

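### Sections 5.1 and 5.3 do not conceal allocation: unmasked site staff can read the next subject's first lens before choosing or qualifying that subject

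*Combined protocol and SAP*

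**What the plan says.** - **Who holds the list (5.1).** "The study site will follow the randomization scheme provided and will complete enrollment according to the randomization list". The same section tells the site not to pre-select subjects. It describes no envelope, central call or web release.
- **How an assignment is obtained (5.3).** The investigator or designee "will consult the lens fitting schedule/randomization scheme to obtain the test article assignment for that subject prior to dispensing", and then "will record the subject's number on the appropriate line of the randomization scheme". This describes a readable list with one line per subject.
- **Blocks (5.1).** "Each block will contain two different lens trial sequences". Only two sequences exist. Block length is not stated. Randomization is stratified by site only.
- **Masking (5.2).** "Investigators and clinical site personnel involved in the data collection will not be masked as to the identity of the investigational product".
- **Recruitment (3.4, 4.3, synopsis).** Candidates come from the site's own database. The site aims for 40 myopes and 40 hyperopes, and for an even spread over two ADD groups.
- **Order of steps (7.2).** Eligibility is settled at step 1.20 and the Randomization ID is recorded at step 1.21.
- **Leaving the study (7.2 step 1.28, 8.2).** A subject with an unacceptable fit at the first fitting is discontinued. A subject who cannot be dispensed because of vision, comfort or fit is withdrawn.
- **Reporting (14.1).** Summaries are by lens type and separately by completion status. Analyses use the per-protocol population.

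**The concern.** Random sequence generation protects a trial only if the people choosing the next subject cannot see what comes next. Here the same unmasked staff hold the list, decide whom to call, and judge eligibility. Filling the refractive and ADD targets gives them a legitimate reason to order calls by optical characteristics, so steering need not be deliberate. Section 5.3 governs breaking the subject's mask and does nothing to hide upcoming lines.

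The crossover limits the damage but does not remove it. A subject who fails on the first lens leaves without trying the second, so the failure is counted against whichever lens came first. If harder-to-fit subjects tend to enter when one lens is next, that lens collects more discontinuations for reasons unrelated to the lens. This study is meant to show the strengths and weaknesses of each product and to inform later trials, so that picture has some value. Steering also makes the two sequence groups differ, and in a 2x2 crossover such a difference cannot be told apart from the carry-over that the washout in section 4.2 is meant to limit.

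**Working it through.** **The plan's own figure.** Section 14.2 states that "approximately 80 eligible subjects will be enrolled into the study at this site and at least 60 subjects will complete this study" and that "the sample size calculation was not based on any power analysis with regard to the primary endpoint". There is no power figure to reproduce. The numbers imply 80 − 60 = 20 withdrawals, or 20/80 = 25%. No withdrawal rate by lens or period is given.

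**Predictability.** With the list readable, every assignment is known and block length is irrelevant. With the list hidden but blocks known to be pairs, the second of each pair is certain and the first is a coin toss: 50% certain, and (0.5 + 1.0)/2 = 75% guessed correctly. In simulated lists of 80, randomly varying blocks of 4, 6 and 8 bring correct guesses down to 68%.

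**Withdrawals by lens: illustration on assumed inputs.** Assume identical lenses, 24 of 80 subjects hard to fit, failure probability p on each lens for those subjects only, and a share s of them placed on lens A first.

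- Withdrawals on A = 24·s·p + 24·(1−s)·(1−p)·p
- Withdrawals on B = 24·(1−s)·p + 24·s·(1−p)·p

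| p | s | A | B | A/B |
|---|---|---|---|---|
| 0.5 | 0.5 (no steering) | 9.0 | 9.0 | 1.0 |
| 0.5 | 0.75 (partial) | 10.5 | 7.5 | 1.4 |
| 0.5 | 1.0 (perfect) | 12.0 | 6.0 | 2.0 |
| 0.3 | 1.0 (perfect) | 7.2 | 5.0 | 1.4 |

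The share s = 0.75 is simply assumed. It does not follow from 75% correct guesses, because it also depends on how many candidates can be queued and how well difficulty is predicted.

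**How the ratio moves.** Under perfect steering A/B = π/(1−π), where π is the share of withdrawals that fall in period 1:

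- π = 0.5 gives 1.0
- π = 0.6 gives 1.5
- π = 2/3 gives 2.0 (the 12 v 6 case, since 12/18 = 2/3)
- π = 0.75 gives 3.0
- π = 1 has no finite value

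**Imperfect prediction.** This was simulated with 80 subjects on one list of random pairs, 20 withdrawals, and 1,000 runs per case.

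| Period-1 share | What staff know | Prediction accuracy | A/B |
|---|---|---|---|
| 2/3 | whole list | 70% | 1.28 (two candidates queued) to 1.43 (all) |
| 2/3 | whole list | 100% | 1.85 to 2.02 |
| 2/3 | second of each pair only | 70% to 100% | 1.10 to 1.57 (two or five queued) |
| 1 | whole list | 70% | 2.2 to 3.0 |

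For comparison, with no steering, 20 withdrawals split 14:6 or more unevenly in 11.5% of trials by chance.

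**Completer means.** Assume hard subjects read 0.10 logMAR worse, p = 0.5, and 40 subjects per sequence.

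- No steering: each sequence has 12 hard subjects, of whom 12 × 0.25 = 3 complete, so the hard share is 3/(28 + 3) = 9.7%.
- Perfect steering: A-first has 24 × 0.25 = 6 hard completers out of 16 + 6 = 22, or 27.3%. B-first has none out of 40. The equally weighted average is 13.6%.
- Shift in the least squares mean: (0.136 − 0.097) × 0.10 = 0.004 logMAR, the same for both lenses. With s = 0.75 it is about 0.001.
- Sequence difference: 0.273 × 0.10 = 0.027 logMAR. With p = 0.3 it is 0.042.

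**Lens difference among completers.** A separate simulation assumed 27 hard subjects reading 0.05 logMAR worse, a between-subject SD of 0.08 and a residual SD of 0.05. With all hard subjects steered to one sequence, the mean lens difference over 4,000 runs was 0.0001 logMAR, which is no bias.

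**The case against.** The strongest reply is that no planned decision depends on this.

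- Each lens is judged against a fixed threshold in completers who wore both lenses, with sequence, period and lens in the model.
- Withdrawal is not an endpoint and is not tested by lens. No carry-over test is planned.
- The shift of at most 0.004 logMAR in the illustration is towards worse acuity, so it works against declaring superiority.
- Both products are marketed competitors, and no motive to favour either is apparent.
- The study is a pilot with exploratory hypotheses, pre-selection is forbidden, and eligibility is settled before the Randomization ID is recorded.

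Most of this stands, and it limits the point to descriptive summaries and sequence balance. Two parts do not answer it. The prohibition has no mechanism behind it, and the order of steps 1.20 and 1.21 does not stop anyone reading the next line beforehand. Nor does fitting sequence as a fixed effect reveal whether a sequence difference comes from selection or from carry-over.

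The block wording is also open to dispute: a block of four with two of each sequence also contains two different sequences. Pairs are the natural reading, not a stated fact. Section 14.1 likewise does not say that each withdrawal will be attributed to the lens being worn, and the illustration ignores the replacement of discontinued subjects that sections 5.2 and 8.2 allow.

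**Conclusion.** The plan lacks allocation concealment. That follows from the text of 5.1, 5.2, 5.3 and 3.4 and needs no assumption. Its consequences are modest: per-lens discontinuation and completion summaries, and any reading of the sequence effect, could reflect who was called when.

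A reader might infer more in three ways that the documents do not support:

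- **That steering can at most double one lens's withdrawals.** Two to one is one scenario, not a limit. It needs perfect prediction and two-thirds of withdrawals in period 1. The range is 1.0 to above 3, and about 1.3 to 1.4 with 70% prediction accuracy at the same period-1 share. None of these inputs is in the documents.
- **That the primary result is biased.** With identical lenses the completer contrast is unbiased, and the means move by about 0.001 to 0.004 logMAR if hard subjects read 0.10 logMAR worse.
- **That sites will steer.** The documents show only that they could.

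Priority is low to moderate: a cheap improvement, not a threat to the main conclusions.

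**What to change.** In 5.1 and 5.3, replace the site-held list with release of one subject's sequence at step 1.21, only after eligibility at step 1.20 has been recorded. Use the EDC system named in 15.1 if it can be configured for this. Otherwise use sequentially numbered, opaque, sealed envelopes prepared by the study biostatistician. Staff still learn each subject's lens in time to use the right fitting guide.

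Replace the block sentence in 5.1 with permuted blocks of randomly varying length, held by the biostatistician and not disclosed to sites. This is the lesser gain (correct guesses fall from about 75% to 68% with blocks of 4, 6 and 8); controlled release does most of the work. Tabulating discontinuations by lens, period and sequence would let a reader see any imbalance.

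The cost is a wording change, a regenerated list, and an EDC field or a set of envelopes. An unfinished block can leave the sequences unequal by a few subjects per site, at most 4 with a block of 8. No extra subjects or visits are needed.
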